9.5 Outcomes

9.5.1 Primary Outcome: The primary objective is to evaluate the effect of MBSR in improving asthma control as assessed by the Asthma Control Questionnaire. *Hypothesis: Asthma control as assessed by the Asthma Control Questionnaire³ will improve significantly more in MBSR than in HLC participants at 18 month follow-up.*

9.5.2 Secondary Outcomes:

1) Asthma-related QoL. *Hypothesis: Asthma-related QoL (AQoL)⁴ will improve more in MBSR than HLC participants from baseline to 18-month follow-up.*

2) Respiratory interoceptive accuracy and its mediating effect on asthma control, QoL, and medication use. *Hypotheses: MBSR will result in improved accuracy (Breath Perception Discrimination Test) at 6-, 12- and 18-months compared with HLC, and will be correlated with improved asthma control, QoL, and medication use.*

3) Lung function (change from baseline in 2-week average morning peak expiratory flow (PEF) and spirometry (Forced Expiratory Volume in 1 second (FEV₁)) at 6-, 12- and 18-months compared with HLC. *Hypotheses: There will be no deterioration, and possibly improvement, in lung function in MBSR participants from baseline to 6-, 12- and 18-months as measured by PEF and FEV₁ as compared with HLC.*

4) Cost-effectiveness in asthma control and management. *Hypothesis: MBSR will be associated with improved cost-effectiveness and improved cost-utility by 18 months as compared with HLC. This will be based on clinical outcomes (e.g., asthma control, QoL, medication use) as well as quality-adjusted life years.*

To conduct cost analysis, we will collect data on number of moderate and severe exacerbations, asthma-related regularly scheduled office visits, acute care visits, hospitalizations, emergency room visits, need for intubation or mechanical ventilation, and other costs during the prior 6 months at baseline, 6-, 12- and 18-month follow-up and associated clinic and hospital costs. The cost data will be determined by two methods: Self-report and actual hospital and health system costs (direct and indirect) obtained from administrative reimbursement data (see Letters of Support from fiscal offices). Brief Treatment Cost Analysis Tool (TCAT), a validated costing tool for counseling interventions,⁸⁹ will be used to calculate cost of delivering MBSR and HLC.

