Secondary Outcomes: Analytic approaches for asthma-related QoL, respiratory interoceptive accuracy, lung function are generally similar to those for the two primary outcomes. To test the mediation effect of respiratory interoceptive accuracy (RIA) on asthma control, QoL, and medication use, we will first compare the difference in RIA by treatment arm. We will then use difference-to-difference approach to analyze the longitudinal associations of the changes in RIA from baseline to each follow-up time point with changes in ACQ, QoL and medication use from baseline to comparable follow-up time points.¹⁰¹⁻¹⁰³ Since we will have measures on three follow-ups, we will use linear mixed models where ACQ, QoL and medication use are treated as outcomes, RIA as the primary predictor, with and without an interaction term between RIA and MBSR indicator. These analyses will help answer whether MBSR intervention improved RIA, and whether between treatment differences in RIA would explain the observed differences in ACQ, QoL and medication use. We will compute incremental cost-effectiveness of MBSR compared with HLC as the difference in average health care costs per study participant over 18 months between MBSR and HLC, divided by the difference in average ACQ. As planned for another NIH-funded cost-effectiveness study (5R01AA009892-19), we will use the overlap between self-reported and administrative reimbursement data to estimate models of administratively estimated inpatient, outpatient, and medication services data as functions of the self-reported data. We will apply these models to all self-reported data to derive the 18-month health care costs of MBSR and HLC. We will calculate the cost of delivering the MBSR and HLC from the Brief Treatment Cost Analysis Tool (TCAT), a validated costing tool for counseling interventions.⁸⁹ Sensitivity analysis: ICER ratios will be computed between baseline and active comparator, with usual considerations of uncertainty evaluated in a probabilistic sensitivity analysis to determine the level to which our cost-effectiveness conclusions are robust.

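### Health care costs are predicted for everyone from self-report alone, with no arm term named, so random recall error equal in both arms would shrink the MBSR-HLC cost difference

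*Combined protocol and SAP*

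**What the plan says.** Section 9.5.2 and the measures table in Section 6.2 collect health care use and cost for the six months before each assessment, from self-report and from administrative reimbursement records.

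Section 9.6 (Secondary Outcomes) combines the two. Where a participant has both sources, the data serve "to estimate models of administratively estimated inpatient, outpatient, and medication services data as functions of the self-reported data". It continues: "We will apply these models to all self-reported data to derive the 18-month health care costs of MBSR and HLC". The ICER is "the difference in average health care costs per study participant over 18 months between MBSR and HLC, divided by the difference in average ACQ". Uncertainty is left to sensitivity analysis, "with usual considerations of uncertainty evaluated in a probabilistic sensitivity analysis".

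The cost of delivering the two programmes comes separately from the TCAT costing tool and is not predicted from self-report.

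The plan does not list the predictors beyond self-report, the functional form or the size of the overlap. It does not say how recorded costs are used once the models are fitted.

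**The concern.** A prediction from self-report alone assumes that, once self-report is known, cost no longer depends on arm. That fails when self-report is a noisy record of true use. The regression then pulls each prediction toward the overall mean, and the two arm means are pulled together with it.

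The health care cost difference feeds the ICER numerator and therefore secondary objective 4. A real saving would be understated, and so would a real extra cost. If the later Section 9.6 analyses (return on investment, intervention-to-care cost ratios) use the same predicted costs, they inherit the error. A probabilistic sensitivity analysis spreads uncertainty around an estimate; it does not recentre a biased one.

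**Working it through.** **Inputs from the documents.** 108 analysed per arm, 216 in all (Section 9.2; 216/254 = 85%). The documents state no cost difference, cost SD, reliability or overlap share, so there is no cost figure to reproduce.

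**Assumptions.** Cost SD 1, true difference 0.40 SD, random overlap of 50%, reliability λ from 0.9 to 0.3; 4,000 simulated trials per setting.

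**Algebra.** Let X be true cost and S = X + e the self-report, with error variance (1−λ)/λ and the same error distribution in both arms.

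- Slope of X on S = 1/(1 + (1−λ)/λ) = λ.
- Difference in predicted means = slope × difference in mean S = λ × true difference.
- Pooling the arms raises the variance of X to 1 + 0.40²/4 = 1.04. The slope is therefore slightly above λ: at λ = 0.5 it is 1.04/(1.04 + 1) = 0.51, and 0.51 × 0.40 = 0.204.

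**Simulation, self-report only, predictions treated as data**

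| λ | λ × 0.40 | Mean estimate | Share of truth | Plain SE | Actual SD | 95% coverage |
|---|---|---|---|---|---|---|
| 0.9 | 0.36 | 0.359 | 90% | 0.130 | 0.131 | 94% |
| 0.7 | 0.28 | 0.287 | 72% | 0.115 | 0.119 | 82% |
| 0.5 | 0.20 | 0.205 | 51% | 0.098 | 0.101 | 47% |
| 0.3 | 0.12 | 0.125 | 31% | 0.076 | 0.082 | 9% |

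A repeat at 60% overlap gave 0.363, 0.283 and 0.205 at λ = 0.9, 0.7 and 0.5, so the overlap share hardly changes the bias. With a true difference of zero, coverage is 94-95%. The low coverage in the table therefore comes mainly from a wrong centre.

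**Other kinds of recall error, arm still omitted**

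- Self-report 30% too low for everyone, no noise: 0.395 against 0.40, coverage 95%. The model corrects it.
- Berkson-type error (true cost scatters around the reported value): 0.40, coverage 93-94% at 50% overlap and 88-93% at 20%.
- Reporting shifted by 0.3 SD in the MBSR arm, in the direction of the true effect (true difference 0.40 or −0.20): 0.88 to 1.73 times the truth.

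**Arm added to the model (random, equal error)**

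| λ | Mean estimate | Plain SE | Actual SD | 95% coverage |
|---|---|---|---|---|
| 0.7 | 0.404 | 0.114 | 0.153 | 85% |
| 0.5 | 0.399 | 0.096 | 0.168 | 73% |

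The bias is gone, but the plain SE is now clearly too small, so prediction error has to be carried through.

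**Price in precision.** With arm in the model the variance is about λ × 2/108 + (1−λ) × 2/(108 × overlap). At λ = 0.7:

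- 50% overlap: 0.01296 + 0.01111 = 0.02407, SD 0.155 (simulated 0.153).
- 20% overlap: 0.01296 + 0.02778 = 0.04074, SD 0.202.
- All costs recorded: √(2/108) = 0.136. Self-report only at 50% overlap: 0.119.

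**The case against.** **Arm is not expressly excluded.** Section 9.6 refers to a method planned for another study, whose specification is not given here, and the model may have covariates that are not listed. That stands as a caution. But elsewhere in Section 9.6 the plan names the arm indicator where it is meant: in the mixed models, the mediation models and the cost-ratio models. The cost-prediction step names only self-report. If arm is intended, one sentence settles it.

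**Imperfect recall need not shrink the difference.** A reader might infer that any recall error pulls it toward zero. The documents do not support that: proportional and Berkson-type errors leave it unbiased, and arm-differential reporting can exaggerate it. Differential reporting is plausible here, because Section 2.2 expects MBSR to change how patients perceive and appraise symptoms.

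**The interval is not shown to be too narrow.** A reader might infer this because predicted costs vary less than real ones. The plan gives no interval formula, the content of its probabilistic sensitivity analysis is open, and without arm the plain SE nearly matches the estimator's own SD (0.098 against 0.101 at λ = 0.5). The interval misses the truth because it is centred wrongly.

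**The magnitude is assumed.** Reliability, overlap and effect size are not in the documents. One total cost stands in for inpatient, outpatient and medication services, whose recall may differ. The overlap may not be random, since Section 4.3 also recruits through community practices, advertisements and a volunteer database. All of this stands, which is why a range is given.

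**Recorded costs may be incomplete.** The documents do not say that the reimbursement data capture care outside the participating systems. This also stands and limits the fix.

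**Conclusion.** The point holds in conditional form. As written, the plan predicts every participant's health care cost from self-report, names no arm term and gives recorded cost no stated role once the models are fitted. If recall error is random around true use and equal in both arms, the health care cost difference shrinks to about λ times the truth: roughly 90, 70 or 50% at an assumed reliability of 0.9, 0.7 or 0.5. If reporting differs by arm, the bias can go either way.

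The neglect of prediction error is minor under the stated model and becomes material once arm is included. The effect is limited to the health care component of cost under one secondary objective. Delivery cost and the primary ACQ analysis are untouched.

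**What to change.** State in Section 9.6:

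1. Use recorded administrative cost for participants and periods where its capture is complete, with a rule for judging completeness that covers care outside the health system.
2. Elsewhere, impute cost from a model with self-report, study arm and arm by self-report. Use multiple imputation with residual draws, or bootstrap the fitting and prediction steps together.
3. Carry that uncertainty into the interval for the cost difference, the ICER and the probabilistic sensitivity analysis.
4. Report the overlap size and the agreement between the two sources by arm.
5. Keep the self-report-only prediction as a sensitivity analysis.

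Sections 9.3 and 9.6 already plan multiple imputation for missing data and covariates, but do not apply it to this step.

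The cost is SAP wording and modest programming on data already collected, plus the check on completeness of capture. The interval widens: at λ = 0.7 the SD of the difference rises from 0.119 to 0.153 with 50% overlap, and to about 0.20 with 20%. The imputation also assumes that, given arm and self-report, participants in the overlap resemble those outside it.

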To compare the cost-effectiveness in asthma control and management between the comparator arms we will compute per-person incremental total cost per defined measure of additional clinical benefit. More specifically, total costs will include direct and indirect costs of intervention, and per-person overall healthcare/hospital care costs over the entire follow-up period to study completion. Key clinical endpoints will include prevention of exacerbations, unscheduled acute care office visits, and emergency room visits, as well as additional quality of life achieved. We will use general linear models to analyze the associations of the person-level intervention cost with ACQ scores, and use the model to predict per-arm required intervention effects. Secondly, we will use linear models to analyze the associations of person-level intervention cost with total healthcare/hospital care cost, and examine whether increases in intervention cost are correlated with lower average healthcare/hospital care cost. This "return-on-investment" analysis will provide information on monetary savings on care cost per dollar of MBSR intervention. Following these steps, we will apply log-linear models to analyzing the intervention-to-care cost ratios, and examine whether they differ by MBSR/HLC status, and other patient/physician factors.

Missing data: For most longitudinal trial studies, missing data and dropouts are unavoidable. To account for potentially differential/informative dropouts, we will apply inverse probability weighting methods that [name] developed for clinical trial studies with [name] and associates.^{104 #2421, 105} This method first estimates the probability of dropout/lost-to-follow-up of a participant based on his/her sociodemographic and health profiles, and uses the estimated probabilities as weights in the regression analysis. This method effectively removes

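### The savings-per-dollar figure comes from regressing care cost on person-level intervention cost; if that cost varies within an arm, the slope is observational, not a randomised effect

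*Combined protocol and SAP*

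**What the plan says.** The return-on-investment sequence is in Section 9.6 of the combined protocol and SAP.

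- First step: "We will use general linear models to analyze the associations of the person-level intervention cost with ACQ scores".
- Second step: "we will use linear models to analyze the associations of person-level intervention cost with total healthcare/hospital care cost", in order to "examine whether increases in intervention cost are correlated with lower average healthcare/hospital care cost". The plan states that this "will provide information on monetary savings on care cost per dollar of MBSR intervention".
- Third step: "we will apply log-linear models to analyzing the intervention-to-care cost ratios". This is the only one of the three that names study arm as a factor.

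On the cost itself, the plan says that "total costs will include direct and indirect costs of intervention" and that TCAT will supply the delivery cost of each programme. It does not say how a programme cost becomes a cost for one participant. Section 5.4 has instructors record the number of classes each participant attends, in both arms.

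Arm-based cost comparisons are also planned in Section 9.6. One is an incremental cost-effectiveness ratio (ICER) whose numerator is the MBSR-HLC difference in mean care cost over 18 months. The other is an incremental total cost per unit of clinical benefit.

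**The concern.** Arm is randomised. The intervention dollars attributed to one person within an arm are not. If those dollars follow attendance, they depend on who chooses or manages to come, and that may be related to health, organisation or access to care. The slope then mixes the effect of MBSR with differences between attenders and non-attenders. The second step names no arm term and no adjustment for baseline health, and carries no exploratory label.

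What is at stake is one published number. This regression is the only stated source of a savings-per-dollar figure, and a payer would read such a figure as the return on funding MBSR. In a pooled regression, HLC dollars would also count towards a figure labelled as per dollar of MBSR.

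**Working it through.** The documents give no result or power figure for this analysis, so there is none to reproduce. The only plan input used is 108 per arm at follow-up (Section 9.2; 254 × 0.85 = 215.9, about 216 in total).

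**1. What the slope estimates.** Let Y be care cost and C intervention cost. The pooled least-squares slope of Y on C is

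b = w·b_between + (1 − w)·b_within,

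where b_between = (mean Y in MBSR − mean Y in HLC) / (mean C in MBSR − mean C in HLC), b_within is the common within-arm slope, and w is the share of the variation in C that lies between arms. Only b_between is protected by randomisation.

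**2. Cost constant within each arm.** Then w = 1, and −b = (care cost HLC − MBSR) / (intervention cost MBSR − HLC). That is the randomised contrast. In simulation with one fixed cost per arm and no true saving, a significant saving appeared in 2.9% of trials (nominal 2.5%).

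**3. Cost proportional to classes attended.** Assumed, not from the documents: cost per class 60 (MBSR) and 40 (HLC), mean attendance 6 of 9, SD 2.5.

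- Difference in mean cost = (60 − 40) × 6 = 120; between-arm variance = (120/2)² = 3,600.
- Within-arm variance = [(60 × 2.5)² + (40 × 2.5)²]/2 = (22,500 + 10,000)/2 = 16,250.
- w = 3,600/(3,600 + 16,250) = 0.18, before attendance is limited to 0-9.

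Under these assumptions about 82% of the weight falls on the non-randomised association.

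**4. How often a false saving appears within one arm.** Assume no true saving and a correlation of −ρ between attendance and care cost for reasons unrelated to the programme. By Fisher's z, P = Φ(atanh(ρ)·√(n − 3) − 1.96), with n = 108 and √105 = 10.247.

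- ρ = 0.1: Φ(1.028 − 1.96) = 18%
- ρ = 0.2: Φ(2.077 − 1.96) = 55%
- ρ = 0.3: Φ(3.172 − 1.96) = 89%

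**5. Simulation of the pooled regression.** 1,500 trials per setting, 108 per arm, costs and attendance as in step 3, lognormal care cost with mean 4,000 and coefficient of variation 1.0 or 1.5. Neither arm nor attendance has any true effect on care cost. Here r is the size of the negative correlation between attendance propensity and log care cost.

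| r | Significant saving, no arm term | With arm term | Mean apparent saving per dollar, no arm term |
|---|---|---|---|
| 0 | 2.3-2.5% | 2.2-2.3% | about 0 |
| 0.1 | 15-17% | 19-21% | 2.2-3.0 |
| 0.2 | 52-58% | 59-67% | 4.4-6.0 |
| 0.3 | 84-89% | 90-95% | 6.6-8.7 |

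Adding an arm term does not help, because it removes the randomised part of the slope and leaves the within-arm part. Comparing care cost by arm in the simulated trials was significant in 3.9-5.5% of them (nominal 5%, two-sided).

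Steps 4 and 5 use different set-ups (one arm with normal data; two arms pooled with skewed data). Their similar percentages show the order of size and do not validate each other.

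**The case against.** **The costing rule is unknown.** Both programmes are group classes that also admit community members (Section 5.2), and MBSR groups hold 20-25 (Section 5.1). A class costs much the same whether or not one participant comes. Section 4.3 adds staff calls after missed classes, which could raise the cost of poor attenders. All of this stands. A reader might infer that cost within an arm differs only through attendance, but the documents do not say so, and the point is therefore conditional. It survives because a person-level cost whose increases are to be examined naturally implies variation within arms. If that variation came from site, cohort or class size instead, the slope would still carry differences that assignment to MBSR did not create.

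**Randomised cost comparisons are planned.** This also stands. A reader might infer that the economic evaluation abandons the randomisation. It does not: the ICER and the incremental cost per benefit compare arms. Neither gives savings per dollar, however, and the inverse probability weighting in Section 9.6 addresses dropout, not selective attendance.

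**The language is mostly associational.** True of the two regression steps. The sentence on savings per dollar turns the association into a return.

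**The percentages are ordinary power for a correlation of a chosen size.** Correct. The documents give no correlation and set no significance criterion for this step, and the sign could be the opposite.

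Two further criticisms are tempting and should not be made. One is that a single cost per arm would be a defect; step 2 of the working shows that it would give the randomised contrast. The other is that zero care cost would leave the cost ratio undefined. Participants must be on inhaled corticosteroids (Section 4.1) and medication is among the costed services (Section 9.6), so a zero over 18 months is unlikely.

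**Conclusion.** The point holds in conditional form and is minor. If person-level intervention cost varies within an arm, the planned slope is a post-randomisation association and should not be reported as money saved per dollar of MBSR. With no true saving, the chance of a significant apparent saving is about 18%, 55% and 89% at assumed attendance-cost correlations of -0.1, -0.2 and -0.3 in 108 participants. If sicker patients attend more, the bias reverses and could mask a real saving. If cost is constant within arm, there is no artefact.

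The same limitation applies to the regression of ACQ on person-level intervention cost. The primary ACQ comparison and the arm-based ICER are untouched.

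**What to change.** In Section 9.6:

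- State how a participant's intervention cost is derived from the TCAT programme cost.
- Define savings per dollar as (mean care cost HLC − MBSR) / (mean delivery cost MBSR − HLC), with participants analysed as randomised and a bootstrap interval.
- If the two delivery costs turn out similar, which is possible because the programmes are matched in weekly sessions and hours, report the two differences separately, because the ratio is then unstable.
- Label the regressions of care cost and of ACQ on person-level intervention cost as descriptive and non-causal.

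This needs no new data, only a small change to the SAP wording. The price is a possibly wide interval around the ratio. The change is safe under either reading of the costing rule: with a constant cost per arm it reproduces the planned point estimate, and with a varying cost it removes the selection.

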5. STUDY INTERVENTIONS

5.1 Interventions, Administration, and Duration

Intervention condition (MBSR): The Mindfulness-Based Stress Reduction (MBSR) program consists of 8 weekly group sessions of 2 ½ hours duration, plus an all-day class on a weekend day during the 6th week.⁸⁴ Classes include systematic and intensive training in mindfulness and its application to everyday life, and the range of challenges arising from chronic diseases, chronic pain conditions, and life stresses of the participants. Formal training in mindfulness is through: (a) body scan, a gradual moving of attention through the body accompanied by awareness of breathing and other bodily sensations while in a lying position, (b) sitting meditation, focusing on the awareness of breathing, bodily sensations, thoughts, and feelings, practiced sitting upright on a chair or cushion, and (c) mindful stretching exercises practiced with awareness of breathing, intended to develop mindfulness during movement. Group exercises and interactions focus on the challenges and achievements that participants experience in integrating mindfulness into their lives and the stressful situations they encounter.

Throughout the 8-week program participants are asked to do up to 45 minutes of home formal meditative-practice-related practice each day, and supported in generalizing skills developed in this way by informal practice. This consists of bringing self-observations and the moment-to-moment non-judgmental awareness into neutral everyday experiences and daily life, and eventually, stressful activities.

The MBSR programs have similar formats, facilities, and structure across the two study sites, UMMS and Miriam Hospital. Miriam Hospital site instructor, [name], follows the established format in the MBSR program and treatment manual developed and validated by the Center for Mindfulness (CFM), University of Massachusetts School of Medicine. Participants in the MBSR courses at each site will include community members and asthma patients. Group size will be 20-25 participants.

Structure: Throughout the duration of the trial, asthma patients will be offered two different scheduling options as classes will be offered twice-weekly by [name] (as well as a substitute teacher). During the course of the active portion of the study, there will be 13 cohorts over 13 quarters.

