Facilities: MBSR classes at the UMass site will be held in the usual MBSR classroom in the Center for Mindfulness. The Miriam Hospital MBSR program will be held at the Lifespan Women's Medicine Collaborative West River facility or in the generously appointed mind-body room (720 sf) at the Lifespan-Miriam Hospital's Collyer Street facility, both located in Providence. Subjects will be given detailed directions to the appropriate facility. Classrooms at either location can accommodate up to 25 patients.

Teacher qualifications: Classes at the UMass site will be taught by the regular CFM MBSR instructors. [name] at the Miriam site has taught mindfulness for over ten years and has broad experience with a wide-array of patient populations in mindfulness. She has received the basic and advanced MBSR certifications from the UMass Center for Mindfulness. [name] will be a "back-up" teacher who will offer 1-2 trainings per year.

She is similarly qualified with over 8 years of experience teaching mindfulness and with basic and advanced certifications from the UMass Center for Mindfulness.

Control condition (HLC): The Healthy Living Course (HLC) consists of 8 weekly group sessions of 2 ½ hour lectures and discussions about health-related topics. This condition controls for the 8-week contact, attention, group support, and other non-MBSR-specific factors that may contribute to its effectiveness. HLC participants in the pilot study reported on the 12-month assessment survey that the HLC was a face-valid and credible program. The HLC will be offered to community members (regardless of whether or not they have asthma) in addition to study participants, consistent with the mix of participants in the MBSR program. As they did successfully in the pilot trial, UMMHC's Marketing and Communications Department will advertise the course and recruit participants from the community. Lectures will be delivered by Health Educators, HLC topics include: healthy nutrition, physical activity/fitness, coping with stress (not including mindfulness), how to get a good night sleep, balancing work and personal life, your communication style, and living a drug-free life (smoking, alcohol, other drugs). Participants will be asked to complete daily assignments taking up to 45 minutes/day to complete related to the topic of each class (e.g., monitoring their diet and physical activity, noting barriers and facilitators) to match for MBSR homework.

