Quality of life	Asthma Quality of Life Questionnaire (AQoL) ⁴ has 32 items assessing impairment in 4 areas of function shown to be important to the QoL of adult patients with asthma (activity limitations, asthma symptoms, emotional function and environmental exposure). Overall QoL is computed by averaging scores on the 4 domains. Items assess the degree to which important activities have been limited by asthma during the last 2 weeks on a 7-point scale (1= maximal impairment, 7= no impairment). Shown to be valid, reliable and sufficiently sensitive to changes in asthma symptoms to capture the effects of an intervention in a clinical trial. ^{4,88} Changes in scores of 0.5 or above represent clinically meaningful improvement in QoL.	■	■	■	■
Respiratory Interoceptive Accuracy (RIA)	The Breath Perception Discrimination Test (BPDT) measures ability to detect small changes in resistive load. This test will be done in the Pulmonary Diagnostic Laboratory at each site and follow procedures outlined in [name] recent publication. ⁵⁹ The test begins with a brief training period to familiarize participants with 5 resistive load settings (including 4 Hans Rudolph very-low-threshold calibrated resistors and 1 blank (no resistance) condition). During the test period, the presentation of the resistor is announced at the onset of a new inspiration for the duration of one full breath cycle. At the conclusion of the breath cycle, participants pause for 5 normal breaths, then the next resistor in the block is presented. The test will be divided into 6 blocks during which there is a random presentation of each resistor so that participants carry out 30 ratings (6 for each condition) over the course of the test. Time to complete: 30 minutes.	■	■	■	■
Exacerbations and Health Care Utilization/Cost	Number of moderate and severe exacerbation, asthma-related regularly scheduled office visits, acute care visits, hospitalizations, emergency room visits, need for intubation or mechanical ventilation, and other costs during the prior 6 months at baseline, 6-, 12- and 18-month follow-up and associated clinic and hospital costs will be determined by two methods: self-report, and actual hospital and health system costs (direct and indirect) obtained from administrative reimbursement data. Brief Treatment Cost Analysis Tool (TCAT), a validated costing tool for counseling interventions, ⁸⁹ will be used to calculate cost of delivering MBSR and HLC.	■	■	■	■

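### The arm comparison of the intervention-to-care cost ratio mixes the price of the course with its effect on care cost, so it cannot show whether MBSR changes care cost

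*Combined protocol and SAP*

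**What the plan says.** Cost-effectiveness is the fourth secondary objective. Section 9.6 sets out several steps for it: an incremental cost-effectiveness ratio, a total cost combining intervention and care, regressions of ACQ score and of care cost on person-level intervention cost, and finally the step at issue: "Following these steps, we will apply log-linear models to analyzing the intervention-to-care cost ratios, and examine whether they differ by MBSR/HLC status". The same sentence goes on to other patient and physician factors.

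The numerator comes from a costing tool. The table in Section 6.2 says that the TCAT "will be used to calculate cost of delivering MBSR and HLC", and Section 9.6 repeats this. The denominator is each person's care cost. Section 9.6 describes models linking self-reported to administrative data and says: "We will apply these models to all self-reported data to derive the 18-month health care costs of MBSR and HLC".

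For the ratio step the plan gives no offset for delivery cost and no rule for reading a higher or lower ratio. Neither delivery costs nor the spread of care costs appear anywhere in the documents.

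**The concern.** The numerator is largely a property of the assigned course, not an outcome of the participant. If one course is more expensive to run, the ratio differs between arms before anyone's use of health care has changed. The null hypothesis of equal ratios is then not the hypothesis of no effect on care cost.

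The direction is also ambiguous. The ratio rises if MBSR is dearer to deliver and also if MBSR lowers care cost. One is unwelcome and the other welcome, and the coefficient does not tell them apart. If MBSR is cheaper to deliver and also saves on care, the two terms offset and the saving can disappear from view.

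At stake is the reading of one secondary economic result. It follows directly on a regression of which the plan says the "analysis will provide information on monetary savings on care cost per dollar of MBSR intervention", so a reader could easily carry that interpretation over to the ratio test.

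**Working it through.** **The plan's own figure.** None exists for this analysis. Only the sample size is borrowed from Section 9.2: 254 recruited, 15% loss, 254 × 0.85 = 215.9, hence 216 analysed and 108 per arm. The 5% level is also from Section 9.2; two-sided testing is assumed.

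**Algebra.** Write I for delivery cost and C for care cost. Since ln(I/C) = ln I − ln C, the arm contrast is

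Δ = ln(k) − ln(c),

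where k is the MBSR:HLC ratio of delivery cost and c the MBSR:HLC ratio of geometric mean care cost. With no care effect c = 1 and Δ = ln(k), which is zero only when k = 1. If *log-linear* means a log-link model instead of a logged outcome, the care term becomes a ratio of mean reciprocal costs, but with delivery cost constant within arm ln(k) still enters in full.

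**Chance of a significant arm difference with no care effect.** Assumptions: 108 per arm, log care cost normal with SD s, no zero costs, delivery cost constant within arm. The standard error is s × √(2/108) = 0.1361 × s. With z = ln(k)/(0.1361 × s), the rejection rate is Φ(z − 1.96) + Φ(−z − 1.96).

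Example: k = 1.5, s = 1.5. ln(1.5) = 0.4055; standard error 0.2041; z = 1.986; Φ(0.026) = 0.51.

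| SD of log care cost | k = 1.05 | k = 1.1 | k = 1.25 | k = 1.5 | k = 2 | k giving 80% |
|---|---|---|---|---|---|---|
| 0.8 | 7.3% | 14.1% | 53.6% | 96.1% | 100% | 1.36 |
| 1.0 | 6.5% | 10.8% | 37.5% | 84.6% | 99.9% | 1.46 |
| 1.2 | 6.0% | 9.0% | 27.7% | 70.0% | 98.9% | 1.58 |
| 1.5 | 5.7% | 7.5% | 19.4% | 51.1% | 92.4% | 1.77 |

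The last column is exp[(1.96 + 0.84) × 0.1361 × s]. Both k and s are assumptions, shown as ranges.

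A simulation (4,000 trials per setting, t-test on the log ratio) agrees. At s = 1.0 it gives 10.9%, 37.5%, 84.3% and 99.8% for k = 1.1, 1.25, 1.5 and 2, and the estimated ratio of ratios returns k each time (1.10, 1.25, 1.51, 2.00). In the same simulated trials a t-test on log care cost alone rejects in 4.8–5.3%.

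**The reverse case.** Suppose MBSR cuts care cost by 30% (c = 0.7) and costs 30% less to deliver (k = 0.7). Then Δ = ln(0.7) − ln(0.7) = 0. With s = 1.0 the ratio test rejects in 5.2% of simulated trials, against about 75% for care cost tested directly.

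**If delivery cost varies by person.** When it varies independently of care cost, the SD of the log ratio becomes √(s² + s_I²), with s_I the SD of log delivery cost. For illustration, s = 1.0 and s_I = 0.66 give 1.20, and the rate at k = 1.5 falls from 85% to 70%. The shift ln(k) itself remains.

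**The case against.** The strongest reply has four parts.

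*The courses are designed to match, so k may be near 1.* Section 5.1 gives both courses eight weekly sessions of the same length and calls the Miriam HLC matched in schedule and structure. This has weight: nothing in the documents supports assuming a large gap, which is why the table starts at k = 1.05. Equality is not established either. The instructors differ in training, and Section 5.1 gives MBSR a further session ("plus an all-day class on a weekend day during the 6th week") while stating only that "The Healthy Living Course (HLC) consists of 8 weekly group sessions". Sections 5.2 and 5.3.2, however, read as giving the all-day class to both.

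*Rejecting equal ratios is correct when k differs from 1.* True: for the quantity modelled it is not an error. It misleads only if read as an effect on care. The plan does not say it will be read that way, but it offers no other reading.

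*The valid quantities are already planned.* Section 9.6 does compute the difference in average 18-month care cost, the delivery cost of each course and their total, with a probabilistic sensitivity analysis. A careful reader could see which component drives the ratio. This lowers the stakes but does not make the ratio comparison interpretable, and the plan specifies no model or test of care cost by arm.

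*The comparison with other patient and physician factors is untouched.* This stands; the point concerns the arm term only.

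Three stronger readings are tempting and not supported. First, that the test will come out significant whenever delivery costs differ: at k = 1.05–1.1 it does so in only about 6–14% of trials. Second, that the ratio or its log will break down for people with zero cost. All participants must be on inhaled corticosteroids (Section 4.1) and the cost models include medication, so zero care cost should be rare; the plan does not say that non-attenders are costed at zero or that anyone is dropped; and a log-link model admits a zero numerator. Third, that this step is itself declared as the test of whether MBSR pays for itself: that purpose is attached to the preceding regression.

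**Conclusion.** The point holds as a flaw in what is being estimated. The arm contrast contains the log of the delivery-cost ratio, so it differs from zero whenever delivery costs differ, its sign cannot be interpreted, and it can conceal a real saving. This part rests on algebra alone.

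How often it would produce a significant result is conditional. Under the stated assumptions the rate stays close to 5% for a gap of 5–10% in delivery cost and becomes large only with bigger gaps; a gap of 36–77% is needed for an 80% chance, depending on the SD. Person-level variation in delivery cost that is independent of care cost would lower these rates.

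The change is worth making, but the importance is limited: this is one step within a secondary economic objective. The primary ACQ analysis, the sample size and the planned incremental cost-effectiveness ratio do not depend on it.

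**What to change.** In Section 9.6, remove the comparison of the intervention-to-care cost ratio by arm. In its place:

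- Compare 18-month care cost per participant between arms as randomised, keeping any zeros, with a method suited to skewed costs. One option is a gamma model with log link, the baseline 6-month cost as covariate, and a bootstrap interval for the difference in means; a two-part model is an alternative if zeros turn out to be common.
- Report TCAT delivery cost per arm separately, as a costing input.
- Add the two to give the total cost that Section 9.6 already defines.

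The roughly 5% rejection rate with no care effect was checked with a t-test on log care cost. The gamma model was not simulated, but it contains no delivery-cost term and so avoids the shift.

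The cost is a change of wording and slight extra analysis. Baseline and follow-up care costs and TCAT costs are already to be collected (Sections 6.2 and 9.5.2).
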